2.2.1 Subgroup Definitions

Analyses will be presented by treatment (█ mg ibudilast, █ mg bumetanide, █ mg ibudilast █ mg bumetanide, or placebo (placebo data will be pooled from the two dose cohorts)) as indicated below and shown in Appendix B.

2.3 Missing Data Conventions

No missing value imputation will be used. That is, all analyses will be based on the observed data (i.e., complete case analysis).

2.4 Interim Analyses

An evaluation of the data by an independent DSMB will take place after 8 patients finish 2 weeks of treatment and 2 weeks of follow-up. The primary responsibilities of the DSMB are to:

1. Review and evaluate the accumulated study data for patient safety, study conduct and progress, and

2. Make recommendation to STALICLA concerning the continuation, modification, or termination of the trial.

Refer to the separate Interim Analysis Plan (IAP) for further details on the interim analyses.

2.5 Study Center Considerations in the Data Analysis

A study center is defined as a treatment administration site or group of treatment administration sites under the Placebo and supervision of the same Principal Investigator (PI). This study will be conducted as a single study center, and therefore, study center considerations are not applicable. In case additional site(s) is (are) added with patients enrolled, the SAP will be revised if needed.

2.6 Documentation and Other Considerations

The data analyses will be conducted using SAS® Software, version 9.4 or later.

3.0 Analysis of Baseline Patient Characteristics

Baseline and demographic characteristics will be summarized by treatment for all patients in the Safety population. Placebo data will be pooled from the two dose groups. Continuous variables will be displayed via summary statistics (n, mean, median, SD, minimum, and maximum). Categorical variables will be summarized via frequency counts and proportions.

A detailed listing of demographics data for each patient will also be provided as shown in Appendix B.

4.0 Analysis of Safety

4.1 Description of Safety Variables

The safety variables for this study are:

- AEs
- Vital Signs and physical examinations
- ECG
- Clinical Laboratory Parameters
- Hearing Assessment

4.2 Analysis of Safety Variables

Adverse Events

Prior to analysis, all AEs will be recorded and classified on the basis of the Medical Dictionary for Regulatory Activities (MedDRA®) terminology. The number and proportion of patients with at least one AE will be summarized by system organ class (SOC) and by preferred term (PT) within SOC for each treatment group.

Similar tables will be provided to display the number and proportion of patients with at least one treatment-related AE, at least one treatment-related AE that led to study treatment discontinuation, at least one serious AE (SAE), at least one treatment-related SAE, at least one treatment-related SAE that led to study treatment discontinuation, at least one AE of special interest (AESI), and at least one AESI that led to study treatment discontinuation by SOC and by PT within SOC. For the purposes of this study, a treatment-related AE is any AE with a relationship to study drug of 'Related'.

In addition, tables will be constructed to summarize AEs by relationship to study drug and by severity.

A separate AE summary table will be constructed to display the number of patients with at least one AE, the number of patients with at least one treatment-related AE, the number of patients with at least one treatment-related AE that led to study treatment discontinuation, the maximum severity of AE by patient, the highest relationship of AE to treatment, the number of patients experiencing at least one SAE, the number of patients with at least one treatment-related SAE, the number of patients with at least one treatment-related SAE that led to study treatment discontinuation, the maximum severity of SAE by patient, the highest relationship of SAE to treatment, the number of patients with at least one AESI, the number of patients with at least one AESI that led to study treatment discontinuation, and the number of deaths.

All AEs will be provided in data listings as shown in Appendix B. AEs having an end date prior to signing the informed consent for this study will not be displayed in the AE data listings.

Vital Signs

The vital signs parameters of interest include temperature, respiratory rate, and orthostatic blood pressure and orthostatic heart rate.

Summary statistics (n, mean, median, SD, minimum, and maximum) will be computed on the raw and change from baseline values for standard vital sign measurements (temperature and respiratory rate) by visit and time for each treatment. The Day 1 prior to treatment time point will serve as baseline. If there are multiple vital signs taken at any time point, then the latest set of vital signs

will be used for the analysis.

Additionally, summary statistics will be computed on the raw and change from baseline values for the orthostatic vital sign measurements (BP and HR) by visit and time for each treatment. The Day 1 prior to treatment time point will serve as baseline. Spaghetti plots of the raw values for orthostatic diastolic BP, orthostatic systolic BP and orthostatic HR will be displayed by patient, time point and treatment.

All vital signs will be provided in data listings as shown in Appendix B. Vital signs taken while standing will be included in the data listings but will not be summarized in the tables.

Physical Examination

All physical examination results will be listed as shown in Appendix B.

ECG

The ECG parameters of interest include HR, PQ, QRS, QT, RR, and QTcF along with information on T and U waves.

As the ECGs are performed in triplicate at Day 1 prior to treatment, the average of the three values for each of the ECG parameters will be used as the baseline value. Summary statistics (n, mean, median, SD, minimum, and maximum) will be computed on the raw and change from baseline values for each parameter by visit and time by treatment and overall. The Day 1 prior to treatment time point will serve as baseline. Spaghetti plots of the raw values for HR and QTcF will be displayed by patient, time point and treatment.

The ECG Interpretations for each of the three ECGs on Day 1 prior to treatment will be used to obtain a Combined Overall ECG Interpretation. The Combined Overall ECG Interpretation in relation to clinical significance at Day 1 prior to treatment (i.e., baseline) will be determined as follows:

- If at least one ECG Interpretation = 'Abnormal – clinically significant', then the Combined Overall ECG Interpretation = 'Abnormal – clinically significant'.
- Else if there are no readings such that ECG Interpretation = 'Abnormal – clinically significant' and there is at least one ECG Interpretation = 'Abnormal – not clinically significant', then the Combined Overall ECG Interpretation = 'Abnormal – not clinically significant'.
- Else if there are no readings such that ECG Interpretation = 'Abnormal – clinically significant' or "Abnormal – not clinically significant" and there is at least one ECG Interpretation = 'Normal', then the Combined Overall ECG Interpretation = 'Normal'.
- Else if all readings have a missing result for ECG Interpretation then the Combined Overall ECG Interpretation is missing.

Additionally, results from the ECG findings will be determined for T wave, U wave, and ECG Interpretation regardless of clinical significance. The Combined Overall T wave, U wave, and ECG Interpretation at Day 1 prior to treatment (i.e. baseline) will be determined by parameter as follows:

- If at least one ECG finding = 'Abnormal', then the Combined Overall finding = 'Abnormal'.
- Else if there are no readings such that ECG finding = 'Abnormal' and there is at least one ECG finding = 'Normal', then the Combined Overall finding = 'Normal'.
- Else if all readings have a missing result for ECG finding then the Combined Overall finding is missing.

Shift tables will be constructed to show the changes in ECG findings in relation to clinical significance (e.g., normal, abnormal clinically significant (CS), abnormal not clinically significant (NCS)) and findings (e.g., normal, abnormal) by parameter from baseline to each visit by treatment and overall.

All ECG data will be provided in data listings as shown in Appendix B.

Laboratory Results

The laboratory tests of interest include blood chemistry, serology, hematology, coagulation, and urinalysis results.

Summary statistics (n, mean, median, SD, minimum, and maximum) will be computed on the raw and change from baseline values for each quantitative laboratory parameter by visit for each treatment group and overall. The screening time point will serve as baseline.

Spaghetti plots of the raw values for sodium, chloride, calcium, magnesium, phosphate, potassium, and platelet count will be displayed by patient, time point and treatment.

For those urinalysis parameters that are qualitative in nature, the number and proportion of patients with each result for each parameter will be summarized by visit and treatment.

Shift tables will be constructed to show the changes in laboratory results in relation to clinical significance (e.g., normal, abnormal clinically significant (CS), abnormal not clinically significant (NCS)) from baseline to each visit. This analysis will be repeated for blood chemistry results for electrolytes (sodium, chloride, calcium, magnesium, phosphate, potassium).

A shift table for blood chemistry results for electrolytes will be constructed to show the changes in laboratory results in relation to range of normal results (e.g., normal, high, low) from baseline to each visit.

The count and proportion of patients with blood chemistry results for electrolytes outside of the normal range (low, high) for each visit will be summarized by treatment and overall.

All laboratory results data will be provided in data listings as shown in Appendix B.

Hearing Assessment

The patient responses to the hearing assessment for each visit will be listed as shown in Appendix B.

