Endpoints	
Primary Endpoints - Safety:
 
The safety outcome measures for this study are as follows:
 
• Incidence, nature and severity of adverse events (AEs).• Incidence, nature and severity of serious adverse events (SAEs).• Incidence, nature and severity of adverse events of special interest (AESIs).• Incidence, nature and severity of AEs leading to treatment discontinuation.• Changes from baseline in SBP, DBP, heart rate (HR) and respiratory rate.• Changes from baseline in orthostatic measurements of blood pressure (BP) and HR.• Changes from baseline in ECG parameters (HR, PQ, QRS, QT, RR and QTcF, along with information on T and U waves).• Incidence of clinically significant ECG abnormalities.• Hearing assessment.• Incidence of clinically relevant laboratory abnormalities, based on hematology, coagulation, blood chemistry and urinalysis test results:
○ Hematology: hemoglobin concentration, hematocrit level, erythrocytes and platelet counts, leucocytes differential (absolute) counts (neutrophils, eosinophils, lymphocytes, monocytes and basophils)○ Coagulation: international normalized ratio (INR), activated partial thromboplastin time (aPTT) and prothrombin time (PT)○ Blood chemistry: C-reactive protein (CRP test), aspartate aminotransferase (AST), alanine aminotransferase (ALT), gamma-glutamyl-transferase (GGT), total and conjugated bilirubin, alkaline phosphatase (ALP), albumin, creatine phosphokinase (CPK), creatinine, urea, total protein, total cholesterol, triglycerides, glucose, sodium, chloride, calcium, magnesium, phosphate, potassium○ Urinalysis: protein, blood, glucose, leucocytes, nitrites, pH and crystals.• Incidence of value outside of the normal ranges and of clinically relevant blood chemistry test results for electrolytes:
○ Sodium, chloride, calcium, magnesium, phosphate, potassium 
Secondary Endpoints - Pharmacokinetics:
 
• [REDACTED] plasma concentration will be evaluated at Days 1, 7, and 14 to 18.• Plasma concentrations of [REDACTED] and associated PK parameters: Area under the plasma concentration-time curve ($AUC_{0-\tau}$, $AUC_{0-\text{last}}$, $AUC_{0-\infty}$), minimum plasma concentration prior to administration (C_{trough}), maximum plasma concentration (C_{max}, $C_{\text{max,ss}}$), time of
-----------	--

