Blinding	
The study will be blinded for patients/caregivers, study personnel with direct interaction with the subjects and vendors, using placebo capsules and tablets that match the active drugs in appearance, labelling and packaging. The total number of capsules making up each dose will be identical for both STP1 dose levels and placebo.
																		

	
Study personnel responsible for receiving the randomization lists and dispensing the assigned treatment will be unblinded. An independent DSMB will be appointed. The DSMB will be blinded to treatment for safety/tolerability assessments (primary outcome) and will advise on the start of 2nd dose level.

Statistical Methods	
For this Phase 1b study, descriptive statistics will be provided for all endpoints by treatment group. For continuous endpoints, summary statistics i.e., n (number of individuals included in the analysis), mean, SD, median, minimum, maximum, Quartile 1, and Quartile 3 will be provided. For categorical endpoints, the number and frequency in each category will be provided.
 
All subjects who have received at least one dose of the combination, whether prematurely withdrawn from the study or not, will be included in the safety analysis.
 
SAFETY and TOLERABILITY
 
The number of patients who report the following events will be summarized for all treated patients:
 
• AE and treatment-related AE.• AE and treatment-related AE that led to study treatment discontinuation.• SAE and treatment related SA.• SAE and treatment related SAE that led to study treatment discontinuation.• AESIs. 
Safety and tolerability are also measured by incidence and severity of AEs, physical examinations, ECG, vital signs, specific laboratory abnormalities and change from baseline in the CSHQ scores in all treated patients.
 
As this study will provide descriptive statistics, there will not be any correction for multiple primary endpoints.
 
PHARMACOKINETICS
 
The PK analysis set will include subjects with at least one sample collected and analyzed for plasma drug concentration. Concentration of each drug in plasma and urine will be listed and summarized by visit and nominal time. The NCA using the sampling mode of PK data and standard descriptive statistics for PK parameters will be calculated using Phoenix WinNonlin software (Certara).

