3.3 OUTCOME MEASURES

3.3.1 SAFETY OUTCOME MEASURES

The safety outcome measures for this study are as follows:

- Incidence, nature and severity of AEs.
- Incidence, nature and severity of SAEs.
- Incidence, nature and severity of AESIs.
- Incidence, nature and severity of AEs leading to treatment discontinuations.
- Changes from baseline in systolic blood pressure (SBP), diastolic blood pressure (DBP), heart rate (HR) and respiratory rate.
- Changes from baseline in orthostatic measurements of BP and HR.
- Changes from baseline in ECG parameters (HR, PQ, QRS, QT, RR and QTcF, along with information on T and U waves).
- Incidence of clinically significant ECG abnormalities.
- Hearing assessment
- Incidence of clinically relevant laboratory abnormalities, based on hematology, blood chemistry and urinalysis test results:
 - Hematology: hemoglobin, hematocrit, erythrocytes, platelet count, leucocytes differential (absolute) counts (neutrophils, eosinophils, lymphocytes, monocytes, basophils).
 - Blood chemistry: aspartate aminotransferase (AST), alanine aminotransferase (ALT), gamma-glutamyltransferase (GGT), total and conjugated bilirubin, alkaline phosphatase (ALP), albumin, creatine phosphokinase (CPK), creatinine, urea, total protein, total cholesterol, triglycerides, sodium, chloride, calcium, magnesium, phosphate, potassium, glucose.
- Incidence of value outside of the normal ranges of blood chemistry test results for electrolytes:
 - Sodium, chloride, calcium, magnesium, phosphate, potassium
- Urinalysis: protein, blood, glucose, leucocytes, nitrites, pH, and presence of crystals.

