6.4 SUMMARIES OF TREATMENT GROUP COMPARABILITY

Demographics, baseline characteristics and all baseline laboratory values will be summarized descriptively by treatment using frequency tables and summary statistics as appropriate. Placebo data will be pooled from the 2 dose groups.

All safety analysis will be based on the safety analysis population.

As appropriate, listings, summary tables and graphs will be provided for safety and tolerability assessments, including:

- Incidence of AEs (overall, by intensity and by relationship to study medications).
- Incidence of SAEs.
- Incidence of AESIs.
- Incidence of discontinuations due to AEs.

- Incidence of laboratory abnormalities (including hematology, clinical chemistry, coagulation and urinalysis parameters).
- Incidence of BP abnormalities.
- Incidence of ECG abnormalities as well ECG changes as compared to baseline measurements.

Further details on the safety parameters are given in [Section 5.1](#). Safety data will be summarized using descriptive statistics using the safety analysis population, which will include all patients treated. Additional safety analyses may be performed as stated in the Statistical Analysis Plan (SAP) for the study.

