8.0 List of Analysis Tables, Figures and Listings

Table No.	Table Title	Included in Final Tables	Shown in Appendix B
1	Patient Disposition	X	X
2	Demographics and Baseline Data Summary Statistics—Continuous Variables (Safety Population)	X	X
3	Demographics and Baseline Data Summary Statistics—Categorical Variables (Safety Population)	X	X
4	Summary of Adverse Events (Safety Population)	X	X
5	Number and Proportion of Patients with Adverse Events (Safety Population)	X	X
6	Number and Proportion of Patients with Treatment-Related Adverse Events (Safety Population)	X	X
7	Number and Proportion of Patients with Treatment-Related Adverse Events that Led to Study Drug Discontinuation (Safety Population)	X	X
8	Number and Proportion of Patients with Serious Adverse Events (Safety Population)	X	X
9	Number and Proportion of Patients with Treatment-Related Serious Adverse Events (Safety Population)	X	X
10	Number and Proportion of Patients with Treatment-Related Serious Adverse Events that Led to Study Drug Discontinuation (Safety Population)	X	X
11	Number and Proportion of Patients with Adverse Events of Special Interest (Safety Population)	X	X
12	Number and Proportion of Patients with Adverse Events of Special Interest that Led to Study Drug Discontinuation (Safety Population)	X	X
13	Number and Proportion of Patients with Adverse Events by Relationship to Study Drug (Safety Population)	X	X
14	Number and Proportion of Patients with Adverse Events by Severity (Safety Population)	X	X
15	Vital Sign Parameter Summary Statistics (Safety Population)	X	X
16	Orthostatic Vital Sign Parameter Summary Statistics (Safety Population)	X	X
17	ECG Parameter Summary Statistics (Safety Population)	X	X
18	ECG Results Shift Table by Visit and Clinical Significance (Safety Population)	X	X
19	ECG Results Shift Table by Visit (Safety Population)	X	X
20	Blood Chemistry Parameter Summary Statistics (Safety Population)	X	X
21	Hematology Parameter Summary Statistics (Safety Population)	X	
22	Coagulation Parameter Summary Statistics (Safety Population)	X	
23	Quantitative Urinalysis Parameter Summary Statistics (Safety Population)	X	
24	Summary of Qualitative Urinalysis Results by Parameter (Safety Population)	X	X

Table No.	Table Title	Included in Final Tables	Shown in Appendix B
25	Blood Chemistry Results Shift Table by Visit and Clinical Significance (Safety Population)	X	X
26	Hematology Results Shift Table by Visit and Clinical Significance (Safety Population)	X	

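### All-cause AEs and SAEs leading to study drug discontinuation, which the protocol asks for, have no SAP table; Table 31 also counts untested patients in its denominator

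*SAP*

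**What the plan says.** The protocol synopsis (Endpoints) lists as a primary safety endpoint "Incidence, nature and severity of AEs leading to treatment discontinuation", and section 3.3.1 repeats it. Neither limits it by causality. The synopsis (Statistical Methods) asks for numbers of patients in paired form: "AE and treatment-related AE that led to study treatment discontinuation" and "SAE and treatment related SAE that led to study treatment discontinuation". Protocol section 6.4 includes "Incidence of discontinuations due to AEs" among the planned safety outputs.

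SAP section 4.2 commits to tables of patients with "at least one treatment-related AE that led to study treatment discontinuation, at least one serious AE (SAE), at least one treatment-related SAE", then treatment-related SAEs that led to discontinuation, AESIs, and AESIs that led to discontinuation. Treatment-related is defined there as a relationship of *Related*. The table list and shells follow this. Table 4 has only treatment-related discontinuation rows, apart from AESIs. Tables 7 and 10 are treatment-related only, and Table 12 is AESI only.

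On electrolytes, the protocol lists values outside the normal range as a safety outcome (synopsis and section 3.3.1). SAP Table 31 reports Low and High counts by visit, and its footnote sets the denominator as all Safety patients in the group. SAP section 2.3 says nothing is imputed and that analyses use observed data.

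**The concern.** Safety and tolerability are the primary objective. The endpoint covers the incidence, nature and severity of events that end treatment, whatever the investigator thinks caused them. The SAP drops the all-cause half of both protocol pairs without giving a reason.

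The protocol can itself produce the uncovered case. Section 3.1.2 discontinues patients whose repeated heart rate or blood pressure falls outside set limits, with no causality condition. Section 5.3.5.5 makes a vital-sign result reportable as an AE if it leads to discontinuation. An out-of-range heart rate is not on the AESI list in section 5.1.3. If such an event is judged *Not related*, Tables 7, 10 and 12 all omit it. The endpoint would then have to be put together from the Y/N flag in Data Listing 3.

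Table 31 also serves a listed primary safety outcome. Because it prints only Low and High over the whole group, a patient without a result at a visit is counted as if not abnormal.

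**Working it through.** **1. Planned group sizes.** The plan's one computed figure is the enrolment of 20. With 16 completers and about 20% dropout, 16 / (1 − 0.20) = 20, so it reproduces. The sizes used below are up to 6 active per dose level and at most 4 pooled placebo (protocol section 6.1), and a minimum of 3 exposed to the highest dose (synopsis). Dropouts stay in the Safety population, so actual denominators could be somewhat larger.

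**2. Request against plan.**

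| Protocol request | SAP output | Covered? |
|---|---|---|
| Related AE leading to discontinuation | Tables 4 and 7 | Yes |
| All-cause AE leading to discontinuation | None by term | No |
| Related SAE leading to discontinuation | Tables 4 and 10 | Yes |
| All-cause SAE leading to discontinuation | None | No |
| Severity of AEs leading to discontinuation | Not in Tables 7, 10 or 12 | No |

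**3. Where an uncovered event would still be seen.** Take a non-AESI event judged *Not related* that stops study drug.
- Tables 5, 13 and 14 count it by term, relationship and severity, and Table 8 counts it by term if it is serious. None of them shows that it ended treatment.
- Table 1 has an Adverse Event row under patient discontinuation, which a patient leaving the study under the stopping rules could enter (protocol section 4.7.1). That row gives no term or severity.
- Table 1's block of reasons for stopping STP1 names pregnancy, non-compliance and unblinding, plus placeholder rows. SAP section 7.1 does promise that each reason will be tabulated.
- Data Listings 1 and 3 carry the reason and the discontinuation flag patient by patient.

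The event itself is therefore not lost. What is missing is a table linking its term and severity to the stop.

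**4. Size of the missing row, with one such patient.** The related row correctly reads 0. The absent all-cause row would read:
- full active group: 1/6 = 16.7%
- pooled placebo: 1/4 = 25.0%
- minimum highest-dose group: 1/3 = 33.3%

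The documents give no rate for such events, so no probability is attached.

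**5. Table 31.** Let x patients be out of range and m untested among N. The table prints x/N, and the observed proportion is x/(N − m). Hence printed = observed × (N − m)/N. With x = 1 and assumed m:

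| N | Printed | Observed, m = 1 | Gap (points) | Observed, m = 2 |
|---|---|---|---|---|
| 6 | 1/6 = 16.7% | 1/5 = 20.0% | 3.3 | 1/4 = 25.0% |
| 4 | 1/4 = 25.0% | 1/3 = 33.3% | 8.3 | 1/2 = 50.0% |
| 3 | 1/3 = 33.3% | 1/2 = 50.0% | 16.7 | 1/1 = 100% |

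With m = 0 the two agree. The counts are right in every case.

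**The case against.** The strongest reply is that the gap is narrow and the information is already there.

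- Protocol section 5.3.4 defines *Related* broadly, and a temporal relationship alone can qualify. Many events that stop drug within two weeks would therefore reach Table 7. Table 12 also picks up AESIs regardless of causality, and these overlap most of the laboratory and orthostatic stopping criteria. This stands, and it limits how often the gap will matter. It does not remove the gap, since *Not related* remains available, for example when another cause is established.
- Section 6.4 of the protocol asks for outputs as appropriate, and Table 1 with Data Listing 3 could meet that. This is fair. The firm requirement rests on the paired wording in the synopsis and on the endpoint definition.
- Two rows in Table 4 would satisfy the synopsis, which asks only for numbers of patients. This is true of the counts, but the endpoint also names nature and severity, and those need the breakdown by term.
- On Table 31, the denominator is openly footnoted, section 2.3 may be aimed mainly at imputation, and the by-visit Tables 18, 19, 24 and 30 carry the same footnote. The shared footnote is a reason to check those tables too. They print the normal categories or every result, however, so a shortfall can be seen by adding the cells. Table 31 on its own does not show one.

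**Conclusion.** The concern holds as a minor one. The SAP omits the all-cause AE and SAE discontinuation summaries that the protocol specifies, and no discontinuation table shows severity. In groups of 3 to 6, a single uncovered event amounts to 16.7% to 33.3% of the group. The impact is small because the analysis is descriptive, every AE is listed with its severity, causality and discontinuation flag, and Table 1 counts reasons for stopping.

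The Table 31 point also holds. One untested patient lowers the printed percentage by 3.3 to 16.7 points when one patient is abnormal. That rests on assumed missing counts, and the effect is zero if everyone is tested. The plan's own dropout assumption of about 20% makes some missing visits foreseeable. Table 30 exposes the shortfall and Table 20 gives n.

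**What to change.** - **SAP section 4.2 and Table 4:** add all-cause rows for AEs and for SAEs leading to study drug discontinuation, beside the existing related rows.
- **Tables 7 and 10:** add all-cause companion tables by SOC and PT, with severity.
- **Table 1:** name Adverse Event in the block of reasons for stopping STP1, in line with SAP section 7.1.
- **Table 31:** use patients with a result at that visit as the denominator and print n. Alternatively, keep the present denominator and add a row for patients not assessed. Tables 47 and 48 already have a row of that name, but it is a response category there, so its meaning in Table 31 would need defining.

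The cost is a short wording change, two rows in Table 4, one named row in Table 1, two companion tables, and a footnote with n (or one row) in Table 31. Severity and the discontinuation flag are already in Data Listing 3, so no new data are needed and trial conduct does not change.
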